Appendix 9 Acceptability Survey for Patients

Instructions: Please answer the questions below to help us understand your experience with the study medication (cobimetinib). For questions with a face, indicate which of the faces best matches how you felt about the medication.

For children who cannot read yet, parents or caregiver, please help us understand your child's experience with the medication. Invite your child to look at the cartoon, ask him or her the questions, and record his or her answer. If your child cannot answer the question, please leave the question blank.

For children who cannot answer for themselves, parents or caregiver, please go directly to questions 7 and 8.

1. How much did you like the taste of the medication?

Taste Acceptability Scale - C

We are interested in better understanding the taste of the study drug that you just took. Please tell us how it tasted to you.

Was it (circle or color in the face that best matches how it tasted to you):

Super
Bad

Really Bad

Bad

Bad

Maybe
Good or
Maybe
Bad

Not sure

Good

Good

Super
Good

Really Good

2. What was the taste of the medication?

- Bitter
- Sweet
- Sour
- Salty

3. How much did you like the feeling of the medication in your mouth?

Taste Acceptability Scale - C

We are interested in better understanding the taste of the study drug that you just took. Please tell us how it tasted to you.

Was it (circle or color in the face that best matches how it tasted to you):

Super
Bad

Really Bad

Bad

Bad

Maybe
Good or
Maybe
Bad

Not sure

Good

Good

Super
Good

Really Good

Appendix 9 Acceptability Survey for Patients (cont.)

4. How difficult was it to swallow the medication?

Taste Acceptability Scale - C

We are interested in better understanding the taste of the study drug that you just took. Please tell us how it tasted to you.

Was it (circle or color in the face that best matches how it tasted to you):

Super
Bad

Really Bad

Bad

Bad

Maybe
Good or
Maybe
Bad

Not sure

Good

Good

Super
Good

Really Good

5. After the medication was not in your mouth anymore, could you still taste the medication?

Yes

No

6. What was the taste you had in your mouth after the medication was gone?

Bitter

Sweet

Sour

Salty

For parent or caregiver of children who cannot answer for themselves:

7. At any time did you have a problem in giving the medication to your child because he or she refused to take it?

Yes

No

8. At any time did you have a problem in giving the planned dose of the medication to your child because he or she threw it up?

Yes

No

Appendix 9 Acceptability Survey for Patients (cont.)

Additional questions for participants receiving the SUSPENSION:

Instructions: Please answer the questions below to help us understand your experience giving the study medication (cobimetinib) at home.

9. Which size medication dispenser (syringe) did you use to administer the medication?
- 3-mL
 - 10-mL
10. How many times did you have to fill the medication dispenser (syringe) to administer the prescribed dose of the medication?
- Once
 - More than once
11. How easy or difficult was it to fill the medication dispenser (syringe) from the bottle?
- Very easy
 - Somewhat easy
 - Somewhat difficult
 - Very difficult

Thank You

Appendix 10 Dosing Tables for Cobimetinib

DOSE LEVEL 1=0.6 MG/KG/DAY, 20 MG TABLETS

Cumulative weekly dose=4.2 mg/kg/week

Doses to be administered on Days 1–21 of cycle; do not administer on Days 22–28.

Weight (kg)	Daily Dose for 7 days	Cumulative Weekly Dose (mg/wk)
20.0–21.4	1 tab 4 d/wk, 0 tab 3 d/wk	80
21.5–26.1	1 tab 5 d/wk, 0 tab 2 d/wk	100
26.2–30.9	1 tab 6 d/wk, 0 tab 1 d/wk	120
31.0–35.7	1 tab daily	140
35.8–40.4	2 tab 1 d/wk, 1 tab 6 d/wk	160
40.5–45.2	2 tab 2 d/wk, 1 tab 5 d/wk	180
45.3–50.0	2 tab 3 d/wk, 1 tab 4 d/wk	200
50.1–54.7	2 tab 4 d/wk, 1 tab 3 d/wk	220
54.8–59.5	2 tab 5 d/wk, 1 tab 2 d/wk	240
59.6–64.2	2 tab 6 d/wk, 1 tab 1 d/wk	260
64.3–69.0	2 tab daily	280
69.1–73.8	3 tab 1 d/wk, 2 tab 6 d/wk	300
73.9–78.5	3 tab 2 d/wk, 2 tab 5 d/wk	320
78.6–83.3	3 tab 3 d/wk, 2 tab 4 d/wk	340
83.4–88.0	3 tab 4 d/wk, 2 tab 3 d/wk	360
88.1–92.8	3 tab 5 d/wk, 2 tab 2 d/wk	380
92.9–97.6	3 tab 6 d/wk, 2 tab 1 d/wk	400
97.7–102.3	3 tab daily	420
102.4–107.1	4 tab 1 d/wk, 3 tab 6 d/wk	440
107.2–111.9	4 tab 2 d/wk, 3 tab 5 d/wk	460
112.0–116.6	4 tab 3 d/wk, 3 tab 4 d/wk	480
116.7–121.4	4 tab 4 d/wk, 3 tab 3 d/wk	500
121.5–126.1	4 tab 5 d/wk, 3 tab 2 d/wk	520
126.2–130.9	4 tab 6 d/wk, 3 tab 1 d/wk	540
131.0–135.7	4 tab daily	560
> 135.7	Contact Medical Monitor	

Appendix 10 Dosing Tables for Cobimetinib (cont.)

DOSE LEVEL = 0.6 MG/KG/DAY, SUSPENSION (4.8 MG/ML)

Doses to be administered on Days 1–21 of cycle; do not administer on Days 22–28.

Weight (kg)	Daily Dose (mL)	Cumulative Weekly Dose (mg)	Weight (kg)	Daily Dose (mL)	Cumulative Weekly Dose (mg)
<7.6	Call Medical Monitor		38.0–41.9	5	168.0
7.6–8.3	1.0	33.6	42.0–45.9	5.5	184.8
8.4–9.1	1.1	37.0	46.0–49.9	6	201.6
9.2–9.9	1.2	40.3	50.0–53.9	6.5	218.4
10.0–10.7	1.3	43.7	54.0–57.9	7	235.2
10.8–11.5	1.4	47.0	58.0–61.9	7.5	252.0
11.6–12.3	1.5	50.4	62.0–65.9	8	268.8
12.4–13.1	1.6	53.8	66.0–69.9	8.5	285.6
13.2–13.9	1.7	57.1	70.0–73.9	9	302.4
14.0–14.7	1.8	60.5	74.0–77.9	9.5	319.2
14.8–15.5	1.9	63.8	78.0–81.9	10	336.0
15.6–16.7	2.0	67.2	82.0–85.9	10.5	352.8
16.8–18.3	2.2	73.9	86.0–89.9	11	369.6
18.4–19.9	2.4	80.6	90.0–93.9	11.5	386.4
20.0–21.5	2.6	87.4	94.0–97.9	12	403.2
21.6–23.1	2.8	94.1	98.0–101.9	12.5	420.0
23.2–25.9	3.0	100.8	102.0–105.9	13	436.8
26.0–29.9	3.5	117.6	106.0–109.9	13.5	453.6
30.0–33.9	4	134.4	110.0–113.9	14	470.4
34.0–37.9	4.5	151.2	114.0–117.9	14.5	487.2
			118.0–121.9	15	504.0
			122.0–125.9	15.5	520.8
			126.0–129.9	16	537.6
			130.0–133.9	16.5	554.4
			>133.9	Call Medical Monitor	

Appendix 10 Dosing Tables for Cobimetinib (cont.)

DOSE LEVEL 2=0.8 MG/KG/DAY, 20 MG TABLETS

Cumulative weekly dose = 5.6 mg/kg/week (wk).

Doses to be administered on Days 1–21 of cycle; do not administer on Days 22–28.

Weight (kg)	Daily Dose for 7 days	Cumulative Weekly Dose (mg/wk)
20.0–23.2	1 tablet (tab) 6 d/wk, 0 tab 1 d/wk	120
23.3–26.7	1 tab daily	140
26.8–30.3	2 tab 1 d/wk, 1 tab 6 d/wk	160
30.4–33.9	2 tab 2 d/wk, 1 tab 5 d/wk	180
34.0–37.5	2 tab 3 d/wk, 1 tab 4 d/wk	200
37.6–41.0	2 tab 4 d/wk, 1 tab 3 d/wk	220
41.1–44.6	2 tab 5 d/wk, 1 tab 2 d/wk	240
44.7–48.2	2 tab 6 d/wk, 1 tab 1 d/wk	260
48.3–51.7	2 tab daily	280
51.8–55.3	3 tab 1 d/wk, 2 tab 6 d/wk	300
55.4–58.9	3 tab 2 d/wk, 2 tab 5 d/wk	320
59.0–62.5	3 tab 3 d/wk, 2 tab 4 d/wk	340
62.6–66.0	3 tab 4 d/wk, 2 tab 3 d/wk	360
66.1–69.6	3 tab 5 d/wk, 2 tab 2 d/wk	380
69.7–73.2	3 tab 6 d/wk, 2 tab 1 d/wk	400
73.3–76.7	3 tab daily	420
76.8–80.3	4 tab 1 d/wk, 3 tab 6 d/wk	440
80.4–83.9	4 tab 2 d/wk, 3 tab 5 d/wk	460
84.0–87.5	4 tab 3 d/wk, 3 tab 4 d/wk	480
87.6–91.0	4 tab 4 d/wk, 3 tab 3 d/wk	500
91.1–94.6	4 tab 5 d/wk, 3 tab 2 d/wk	520
94.7–98.2	4 tab 6 d/wk, 3 tab 1 d/wk	540
98.3–101.7	4 tab daily	560
101.8–105.3	5 tab 1 d/wk, 4 tab 6 d/wk	580
105.4–108.9	5 tab 2 d/wk, 4 tab 5 d/wk	600
109.0–112.5	5 tab 3 d/wk, 4 tab 4 d/wk	620
112.6–116.0	5 tab 4 d/wk, 4 tab 3 d/wk	640
116.1–119.6	5 tab 5 d/wk, 4 tab 2 d/wk	660
119.7–123.2	5 tab 6 d/wk, 4 tab 1 d/wk	680
123.3–126.7	5 tab daily	700
> 126.8	Contact Medical Monitor	

Appendix 10 Dosing Tables for Cobimetinib (cont.)

DOSE LEVEL 2=0.8 MG/KG/DAY, SUSPENSION (4.8 MG/ML)

Doses to be administered on Days 1–21 of cycle; do not administer on Days 22–28.

Weight (kg)	Daily Dose (mL)	Cumulative Weekly Dose (mg)	Weight (kg)	Daily Dose (mL)	Cumulative Weekly Dose (mg)
<5.7	Call Medical Monitor		34.5–37.4	6	201.6
5.7–6.2	1.0	33.6	37.5–40.4	6.5	218.4
6.3–6.8	1.1	37.0	40.5–43.4	7	235.2
6.9–7.4	1.2	40.3	43.5–46.4	7.5	252.0
7.5–8.0	1.3	43.7	46.5–49.4	8	268.8
8.1–8.6	1.4	47.0	49.5–52.4	8.5	285.6
8.7–9.2	1.5	50.4	52.5–55.4	9	302.4
9.3–9.8	1.6	53.8	55.5–58.4	9.5	319.2
9.9–10.4	1.7	57.1	58.5–61.4	10	336.0
10.5–11.0	1.8	60.5	61.5–64.4	10.5	352.8
11.1–11.6	1.9	63.8	64.5–67.4	11	369.6
11.7–12.5	2.0	67.2	67.5–70.4	11.5	386.4
12.6–13.7	2.2	73.9	70.5–73.4	12	403.2
13.8–14.9	2.4	80.6	73.5–76.4	12.5	420.0
15.0–16.1	2.6	87.4	76.5–79.4	13	436.8
16.2–17.3	2.8	94.1	79.5–82.4	13.5	453.6
17.4–19.4	3.0	100.8	82.5–85.4	14	470.4
19.5–22.4	3.5	117.6	85.5–88.4	14.5	487.2
22.5–25.4	4	134.4	88.5–91.4	15	504.0
25.5–28.4	4.5	151.2	91.5–94.4	15.5	520.8
28.5–31.4	5	168.0	94.5–97.4	16	537.6
31.5–34.4	5.5	184.8	97.5–100.4	16.5	554.4
			100.5–103.4	17	571.2
			103.5–106.4	17.5	588.0
			106.5–109.4	18	604.8
			109.5–112.4	18.5	621.6
			>112.4	Call Medical Monitor	

Appendix 10 Dosing Tables for Cobimetinib (cont.)

DOSE LEVEL 3= 1 MG/KG/DAY, 20 MG TABLETS

Cumulative weekly dose = 7 mg/kg/week

Doses to be administered on Days 1–21 of cycle; do not administer on Days 22–28.

Weight (kg)	Daily Dose for 7 days	Cumulative Weekly Dose (mg/wk)
20.0–21.4	1 tab daily	140
21.5–24.2	2 tab 1 d/wk, 1 tab 6 d/wk	160
24.3–27.1	2 tab 2 d/wk, 1 tab 5 d/wk	180
27.2–30.0	2 tab 3 d/wk, 1 tab 4 d/wk	200
30.1–32.8	2 tab 4 d/wk, 1 tab 3 d/wk	220
32.9–35.7	2 tab 5 d/wk, 1 tab 2 d/wk	240
35.8–38.5	2 tab 6 d/wk, 1 tab 1 d/wk	260
38.6–41.4	2 tab daily	280
41.5–44.2	3 tab 1 d/wk, 2 tab 6 d/wk	300
44.3–47.1	3 tab 2 d/wk, 2 tab 5 d/wk	320
47.2–50.0	3 tab 3 d/wk, 2 tab 4 d/wk	340
50.1–52.8	3 tab 4 d/wk, 2 tab 3 d/wk	360
52.9–55.7	3 tab 5 d/wk, 2 tab 2 d/wk	380
55.8–58.5	3 tab 6 d/wk, 2 tab 1 d/wk	400
58.6–61.4 ^a	3 tab daily	420
61.5–64.2	4 tab 1 d/wk, 3 tab 6 d/wk	440
64.3–67.1	4 tab 2 d/wk, 3 tab 5 d/wk	460
67.2–70.0	4 tab 3 d/wk, 3 tab 4 d/wk	480
70.1–72.8	4 tab 4 d/wk, 3 tab 3 d/wk	500
72.9–75.7	4 tab 5 d/wk, 3 tab 2 d/wk	520
75.8–78.5	4 tab 6 d/wk, 3 tab 1 d/wk	540
78.6–81.4	4 tab daily	560
81.5–84.2	5 tab 1 d/wk, 4 tab 6 d/wk	580
84.3–87.1	5 tab 2 d/wk, 4 tab 5 d/wk	600
87.2–90.0	5 tab 3 d/wk, 4 tab 4 d/wk	620
90.1–92.8	5 tab 4 d/wk, 4 tab 3 d/wk	640
92.9–95.7	5 tab 5 d/wk, 4 tab 2 d/wk	660
95.8–98.5	5 tab 6 d/wk, 4 tab 1 d/wk	680
98.6–101.4	5 tab daily	700
101.5–104.2	6 tab 1 d/wk, 5 tab 6 d/wk	720
104.3–107.1	6 tab 2 d/wk, 5 tab 5 d/wk	740
107.2–110.0	6 tab 3 d/wk, 5 tab 4 d/wk	760
110.1–112.8	6 tab 4 d/wk, 5 tab 3 d/wk	780
112.9–115.7	6 tab 5 d/wk, 5 tab 2 d/wk	800
115.8–118.5	6 tab 6 d/wk, 5 tab 1 d/wk	820
118.6–121.4	6 tab daily	840

^a For patients > 60 kg, contact Medical Monitor.

Appendix 10 Dosing Tables for Cobimetinib (cont.)

DOSE LEVEL 3=1 MG/KG/DAY, SUSPENSION (4.8 MG/ML)

Doses to be administered on Days 1–21 of cycle; do not administer on Days 22–28.

Weight (kg)	Daily Dose (mL)	Cumulative Weekly Dose (mg)	Weight (kg)	Daily Dose (mL)	Cumulative Weekly Dose (mg)
<4.6	Call Medical Monitor		44.4–46.7	9.5	319.2
4.6–5.0	1.0	33.6	46.8–49.1	10	336.0
5.1–5.5	1.1	37.0	49.2–51.5	10.5	352.8
5.6–5.9	1.2	40.3	51.6–53.9	11	369.6
6.0–6.4	1.3	43.7	54.0–56.3	11.5	386.4
6.5–6.9	1.4	47.0	56.4–58.7	12	403.2
7.0–7.4	1.5	50.4	58.8–61.1 ^a	12.5	420.0
7.5–7.9	1.6	53.8	61.2–63.5	13	436.8
8.0–8.3	1.7	57.1	63.6–65.9	13.5	453.6
8.4–8.8	1.8	60.5	66.0–68.3	14	470.4
8.9–9.3	1.9	63.8	68.4–70.7	14.5	487.2
9.4–10.0	2.0	67.2	70.8–73.1	15	504.0
10.1–11.0	2.2	73.9	73.2–75.5	15.5	520.8
11.1–11.9	2.4	80.6	75.6–77.9	16	537.6
12.0–12.9	2.6	87.4	78.0–80.3	16.5	554.4
13.0–13.9	2.8	94.1	80.4–82.7	17	571.2
14.0–15.5	3.0	100.8	82.8–85.1	17.5	588.0
15.6–17.9	3.5	117.6	85.2–87.5	18	604.8
18.0–20.3	4	134.4	87.6–89.9	18.5	621.6
20.4–22.7	4.5	151.2	90.0–92.3	19	638.4
22.8–25.1	5	168.0	92.4–94.7	19.5	655.2
25.2–27.5	5.5	184.8	94.8–97.1	20	672.0
27.6–29.9	6	201.6	97.2–99.5	20.5	688.8
30.0–32.3	6.5	218.4	99.6–101.9	21	705.6
32.4–34.7	7	235.2	102.0–104.3	21.5	722.4
34.8–37.1	7.5	252.0	104.4–106.7	22	739.2
37.2–39.5	8	268.8	106.8–109.1	22.5	756.0
39.6–41.9	8.5	285.6	109.2–111.5	23	772.8
42.0–44.3	9	302.4	111.6–113.9	23.5	789.6
			114.0–116.3	24	806.4

^a For patients >60 kg, contact Medical Monitor.

Appendix 10 Dosing Tables for Cobimetinib (cont.)

DOSE LEVEL 4=1.33 MG/KG/DAY, 20 MG TABLETS

Cumulative weekly dose=9.31 mg/kg/week

Doses to be administered on Days 1–21 of cycle; do not administer on Days 22–28.

Weight (kg)	Daily Dose for 7 days	Cumulative Weekly Dose (mg/wk)
20.0–20.4	2 tab 2 d/wk, 1 tab 5 d/wk	180
20.5–22.5	2 tab 3 d/wk, 1 tab 4 d/wk	200
22.6–24.7	2 tab 4 d/wk, 1 tab 3 d/wk	220
24.8–26.8	2 tab 5 d/wk, 1 tab 2 d/wk	240
26.9–29.0	2 tab 6 d/wk, 1 tab 1 d/wk	260
29.1–31.1	2 tab daily	280
31.2–33.2	3 tab 1 d/wk, 2 tab 6 d/wk	300
33.3–35.4	3 tab 2 d/wk, 2 tab 5 d/wk	320
35.5–37.5	3 tab 3 d/wk, 2 tab 4 d/wk	340
37.6–39.7	3 tab 4 d/wk, 2 tab 3 d/wk	360
39.8–41.8	3 tab 5 d/wk, 2 tab 2 d/wk	380
41.9–44.0	3 tab 6 d/wk, 2 tab 1 d/wk	400
44.1–46.1	3 tab daily	420
46.2–48.3	4 tab 1 d/wk, 3 tab 6 d/wk	440
48.4–50.4	4 tab 2 d/wk, 3 tab 5 d/wk	460
50.5–52.6	4 tab 3 d/wk, 3 tab 4 d/wk	480
52.7–54.7	4 tab 4 d/wk, 3 tab 3 d/wk	500
54.8–56.9	4 tab 5 d/wk, 3 tab 2 d/wk	520
57.0–59.0	4 tab 6 d/wk, 3 tab 1 d/wk	540
59.1–61.2 ^a	4 tab daily	560
61.3–63.3	5 tab 1 d/wk, 4 tab 6 d/wk	580
63.4–65.5	5 tab 2 d/wk, 4 tab 5 d/wk	600
65.6–67.6	5 tab 3 d/wk, 4 tab 4 d/wk	620
67.7–69.8	5 tab 4 d/wk, 4 tab 3 d/wk	640
69.9–71.9	5 tab 5 d/wk, 4 tab 2 d/wk	660
72.0–74.1	5 tab 6 d/wk, 4 tab 1 d/wk	680
74.2–76.2	5 tab daily	700
76.3–78.4	6 tab 1 d/wk, 5 tab 6 d/wk	720
78.5–80.5	6 tab 2 d/wk, 5 tab 5 d/wk	740
80.6–82.7	6 tab 3 d/wk, 5 tab 4 d/wk	760
82.8–84.8	6 tab 4 d/wk, 5 tab 3 d/wk	780
84.9–87.0	6 tab 5 d/wk, 5 tab 2 d/wk	800
87.1–89.1	6 tab 6 d/wk, 5 tab 1 d/wk	820
89.2–91.2	6 tab daily	840

^a For patients >60 kg, contact Medical Monitor.

Appendix 10 Dosing Tables for Cobimetinib (cont.)

DOSE LEVEL 4= 1.33 MG/KG/DAY, SUSPENSION (4.8 MG/ML)

Doses to be administered on Days 1–21 of cycle; do not administer on Days 22–28.

Weight (kg)	Daily Dose (mL)	Cumulative Weekly Dose (mg)	Weight (kg)	Daily Dose (mL)	Cumulative Weekly Dose (mg)
<4.9	Call Medical Monitor		37.0–38.7	10.5	352.8
4.9–5.2	1.4	47.0	38.8–40.6	11	369.6
5.3–5.5	1.5	50.4	40.7–42.4	11.5	386.4
5.6–5.9	1.6	53.8	42.5–44.2	12	403.2
6.0–6.3	1.7	57.1	44.3–46.0	12.5	420.0
6.4–6.6	1.8	60.5	46.1–47.8	13	436.8
6.7–7.0	1.9	63.8	47.9–49.6	13.5	453.6
7.1–7.5	2.0	67.2	49.7–51.4	14	470.4
7.6–8.3	2.2	73.9	51.6–53.2	14.5	487.2
8.4–9.0	2.4	80.6	53.2–55.0	15	504.0
9.1–9.7	2.6	87.4	55.1–56.8	15.5	520.8
9.8–10.4	2.8	94.1	56.9–58.6	16	537.6
10.5–11.7	3.0	100.8	58.7–60.4 ^a	16.5	554.4
11.8–13.5	3.5	117.6	60.5–62.2	17	571.2
13.6–15.3	4	134.4	62.3–64.0	17.5	588.0
15.4–17.1	4.5	151.2	64.1–65.8	18	604.8
17.2–18.9	5	168.0	65.9–67.6	18.5	621.6
19.0–20.7	5.5	184.8	67.7–69.4	19	638.4
20.8–22.5	6	201.6	69.5–71.2	19.5	655.2
22.6–24.3	6.5	218.4	71.3–73.0	20	672.0
24.4–26.1	7	235.2	73.1–74.8	20.5	688.8
26.2–27.9	7.5	252.0	74.9–76.6	21	705.6
28.0–29.7	8	268.8	76.7–78.4	21.5	722.4
29.8–31.5	8.5	285.6	78.5–80.3	22	739.2
31.6–33.3	9	302.4	80.4–82.1	22.5	756.0
33.4–35.1	9.5	319.2	82.2–83.9	23	772.8
35.2–36.9	10	336.0	84.0–85.7	23.5	789.6
			85.8–87.5	24	806.4

^a For patients >60 kg, contact Medical Monitor.

Appendix 10 Dosing Tables for Cobimetinib (cont.)

DOSE LEVEL –1 (MINUS ONE)=0.45 MG/KG/DAY, 20 MG TABLETS

Cumulative weekly dose=4.2 mg/kg/week

Doses to be administered on Days 1–21 of cycle; do not administer on Days 22–28.

Weight (kg)	Daily Dose for 7 days	Cumulative Weekly Dose (mg/wk)
20–22.2	1 tab 3 d/wk, 0 tab 4 d/wk	60
22.3–28.5	1 tab 4 d/wk, 0 tab 3 d/wk	80
28.6–34.9	1 tab 5 d/wk, 0 tab 2 d/wk	100
35.0–41.2	1 tab 6 d/wk, 0 tab 1 d/wk	120
41.3–47.6	1 tab daily	140
47.7–53.9	2 tab 1 d/wk, 1 tab 6 d/wk	160
54.0–60.3	2 tab 2 d/wk, 1 tab 5 d/wk	180
60.4–66.6	2 tab 3 d/wk, 1 tab 4 d/wk	200
66.7–73.0	2 tab 4 d/wk, 1 tab 3 d/wk	220
73.1–79.3	2 tab 5 d/wk, 1 tab 2 d/wk	240
79.4–85.7	2 tab 6 d/wk, 1 tab 1 d/wk	260
85.8–92.0	2 tab daily	280
92.1–98.4	3 tab 1 d/wk, 2 tab 6 d/wk	300
98.5–104.7	3 tab 2 d/wk, 2 tab 5 d/wk	320
104.8–111.1	3 tab 3 d/wk, 2 tab 4 d/wk	340
111.2–117.4	3 tab 4 d/wk, 2 tab 3 d/wk	360
117.5–123.8	3 tab 5 d/wk, 2 tab 2 d/wk	380
123.9–130.1	3 tab 6 d/wk, 2 tab 1 d/wk	400
130.2–136.5	3 tab daily	420
> 136.5	Contact Medical Monitor	

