3.3.1.1 Rationale for Tablet and Suspension Dosing Strategy

Cobimetinib has good solubility in water (0.74 mg/mL, at 37°C). A mass balance study in humans has shown that the fraction of dose absorbed is 0.88, indicating high fraction absorbed and hence permeability. Given the high solubility and permeability of cobimetinib, differences due to formulation change are not anticipated. During development of cobimetinib in adult populations, it was seen that different formulations provided comparable exposures (see cobimetinib Investigator's Brochure), and that cobimetinib absorption was not dissolution-rate limited. Hence, the suspension is expected to provide similar exposures as would be obtained upon administration of the tablet, and therefore equivalent doses administered to pediatric patients will provide comparable exposures. As bioequivalence has not been directly proven between the existing tablet and powder for suspension formulations in a relative bioavailability study, the Sponsor will initiate dose escalation for the suspension at least one dose level below that of the tablet MTD/MAD to ensure study drug administration via suspension does not result in overexposure or excessive toxicity.

Both tablet and suspension formulations are being utilized to ensure adequate age-appropriate dosing for the study. Enrollment to receive the tablet will be restricted to patients ≥ 6 years of age due to the size of the tablet. Enrollment to receive the tablet will further be restricted to patients weighing ≥ 20 kg, because tablet dosing (defined in [Appendix 10](#)) in patients < 20 kg could potentially cause excessive variation in cumulative administered dose per kilogram ($> 10\%$) within a dose level cohort.

To ensure that patients treated with tablets receive a cumulative dose most closely approximating their body weight, patients will be assigned a cumulative weekly dose in 20-mg increments, with distribution of tablets as evenly as possible throughout the week. For example, if a patient's dose is 60 mg in a week, the dosing would be 20 mg on Days 1, 3, and 5 of that week. Given the $T_{1/2}$ of cobimetinib (approximately 2 days), the intermittent dosing of cobimetinib is not expected to result in significant fluctuations in the average cobimetinib concentrations, and steady state exposures will be achieved approximately 10 days after start of dosing.

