For patients who receive tablets, cobimetinib will be administered on Days 1-21 of each cycle as whole 20-mg tablets. For pediatric patients, a cumulative weekly dose (rounded to nearest 20 mg) based on weight and dose level will be determined, and daily dose in whole tablets will be extrapolated from this dose. **Investigators must not calculate the dose on their own but must use the dosing charts in Appendix 10** to determine the correct dose amount and frequency based on dose level and patient weight.

For patients who receive suspension, cobimetinib will be administered using either a 3-mL or a 10-mL oral dispenser. The patient will take the same dose on Days 1–21 of each cycle. Investigators must not calculate the dose on their own but must use the dosing charts in [Appendix 10](#) to determine the correct dose amount based on dose level and patient weight. Note that cobimetinib should not be administered through a nasogastric tube on this study, given that the adsorptive properties of nasogastric tubes for cobimetinib are unknown.

Cobimetinib should be taken at approximately the same time each day, no earlier than 1 hour before and no later than 4 hours after the usual dosing time. On study visit days, the dose of cobimetinib will be taken in the clinic, after pretreatment assessments have been performed.

Patients or their caregivers must record the time and date they take each dose of cobimetinib in a medication diary. Cobimetinib can be administered at the same time as food, or on an empty stomach. However, suspension cobimetinib should only be administered with the supplied oral dispenser(s) and should not be mixed into food, milk, or juice. Tablets may not be crushed or cut. Missed doses should also be recorded. Patients and their caregivers will be instructed to bring all unused study drug and the study drug diary to each study visit for assessments of compliance.

If a dose of cobimetinib is missed (i.e., not taken within 4 hours after the scheduled dosing time), the patient should resume dosing with the next scheduled dose. Missed or vomited doses will not be made up.

If cobimetinib treatment has been interrupted for more than 28 days for whatever reason (including adverse events), the patient will be considered to have discontinued from study drug and will enter the treatment follow-up period.

Guidelines for dosage modification and treatment interruption or discontinuation are provided in [Table 2](#).

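### Two small errors in the binding Appendix 10 dosing charts: the Dose Level -1 tablet heading prints 4.2 instead of 3.15 mg/kg/week, and the Dose Level 4 suspension chart omits 51.5 kg and lists 53.2 kg twice

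*Combined protocol and SAP*

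**What the plan says.** Section 4.3.2 sets the tablet rule: "a cumulative weekly dose (rounded to nearest 20 mg) based on weight and dose level will be determined". It then takes the arithmetic away from the site, for tablets and suspension alike: "Investigators must not calculate the dose on their own but must use the dosing charts" of Appendix 10.

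The appendix holds ten charts, one tablet and one suspension chart for each of five dose levels. Each tablet chart has a title with the daily dose and a sub-heading with the weekly dose. The Dose Level -1 tablet chart is titled "DOSE LEVEL –1 (MINUS ONE)=0.45 MG/KG/DAY, 20 MG TABLETS", and its sub-heading is "Cumulative weekly dose=4.2 mg/kg/week". The same sub-heading stands over the Dose Level 1 tablet chart, which is for 0.6 mg/kg/day. For comparison, the Dose Level 4 tablet chart (1.33 mg/kg/day) carries "Cumulative weekly dose=9.31 mg/kg/week".

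In the Dose Level 4 suspension chart (1.33 mg/kg/day, 4.8 mg/mL), three consecutive rows give 14 mL for 49.7–51.4 kg, 14.5 mL for 51.6–53.2 kg and 15 mL for 53.2–55.0 kg.

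**The concern.** A chart that replaces calculation has to give exactly one dose for every weight it spans, and its title, heading and rows have to agree. These two charts fail in different ways.

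On the Level -1 tablet chart, title and sub-heading contradict each other. Level -1 is where a Level 1 patient goes when the dose must be reduced, so the wrong heading restates the dose that was just found too high. It can mislead anyone who checks a row against it. It could also mislead at the one step that has no chart: Section 5.1.1 calls for a 25% reduction from the lowest defined level. Working from the printed heading gives 4.2 x 0.75 = 3.15 mg/kg/week, which is the current Level -1 dose and so no reduction. Working from the correct figure gives 3.15 x 0.75 = 2.36. Someone who starts from the patient's row avoids this.

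On the Level 4 suspension chart, a compliant site has no permitted dose at 51.5 kg and two at 53.2 kg. Both weights lie below the 60 kg above which the chart's footnote refers the site to the Medical Monitor, so the chart offers no fallback. Section 4.3.2 has patients weighed each cycle and the dose adjusted, so the bands are consulted repeatedly.

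**Working it through.** **Inputs.** Daily doses, weekly sub-headings, weight bands and row doses from Appendix 10; rounding of the weekly tablet dose to 20 mg from Section 4.3.2; suspension strength 4.8 mg/mL from the chart titles.

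**1. Tablet sub-headings: weekly dose = daily dose x 7.**

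| Dose level | Daily (mg/kg) | x 7 | Printed weekly |
|---|---|---|---|
| 1 | 0.6 | 4.2 | 4.2 |
| 2 | 0.8 | 5.6 | 5.6 |
| 3 | 1.0 | 7.0 | 7 |
| 4 | 1.33 | 9.31 | 9.31 |
| -1 | 0.45 | **3.15** | **4.2** |

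Four of the five are reproduced. Level -1 is not: 4.2/3.15 = 1.33, one third too high.

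**2. Which Level -1 figure do the rows follow?** Weight x weekly rate, rounded to 20 mg:

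- 20.0 kg: 20 x 3.15 = 63, rounds to 60 (the row says 60). With 4.2: 84, rounds to 80.
- 40 kg: 40 x 3.15 = 126, rounds to 120 (the row says 120). With 4.2: 168, rounds to 160, which is the Level 1 row.
- 136.5 kg: 136.5 x 3.15 = 429.98, rounds to 420 (the row says 420).

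Over every 0.1 kg from 20.0 to 136.5 kg (1,166 weights, 19 rows), 3.15 reproduces the printed dose each time and 4.2 never does. The title and rows are right; only the sub-heading is wrong.

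**3. Continuity of the weight bands.** The ten charts hold 380 dose rows: 144 tablet (19 + 25 + 30 + 36 + 34) and 236 suspension (34 + 43 + 47 + 58 + 54), both in the order Levels -1, 1, 2, 3, 4. That gives 380 - 10 = 370 row-to-row joins. Of these, 368 step by 0.1 kg. The other two are both in the Level 4 suspension chart:

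- 51.4 to 51.6: a step of 0.2, so 51.5 kg has no row.
- 53.2 to 53.2: a step of 0.0, so 53.2 kg is in two rows.

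**4. Intended dose at those weights.** mL = weight x 1.33 / 4.8, to the nearest 0.5 mL as in the neighbouring rows:

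| Weight (kg) | Target (mL) | Nearest 0.5 mL | Lower neighbour | Upper neighbour |
|---|---|---|---|---|
| 51.4 | 14.24 | 14 | | |
| 51.5 | 14.27 | 14.5 | 14 mL: -1.9% | 14.5 mL: +1.6% |
| 53.2 | 14.74 | 14.5 | 14.5 mL: -1.6% | 15 mL: +1.8% |
| 53.3 | 14.77 | 15 | | |

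The rounding midpoints agree: 14.25 x 4.8/1.33 = 51.43 kg and 14.75 x 4.8/1.33 = 53.23 kg. The 14.5 mL band should therefore run from 51.5 to 53.2 kg, and the 15 mL band should start at 53.3 kg.

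**5. Scale.** At nearby band ends the chart's ordinary rounding is about as large: 13 mL at 47.8 kg (target 13.24 mL) is -1.85%, and 13 mL at 46.1 kg (target 12.77 mL) is +1.77%. At lower weights it is larger: 3 mL at 11.7 kg (target 3.24 mL) is -7.5%, and 3.5 mL at 11.8 kg (target 3.27 mL) is +7.0%.

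**The case against.** The strongest reply is that this is proofreading. No tabulated Level -1 dose is wrong. Sites are told to read the rows and not to calculate, so the only way to be misled by the heading is to do what Section 4.3.2 forbids. The dose-level table in Section 3.1.1.2 also gives 0.45 mg/kg correctly. This largely stands, with one exception: the 25% reduction in Section 5.1.1 has no chart and has to be calculated by someone.

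The suspension errors need a narrow set of circumstances. The patient must be dosed by weight (those aged 18 or over at entry take a flat 60 mg), be on suspension at 1.33 mg/kg although large enough for tablets, and weigh exactly 51.5 or 53.2 kg. Suspension escalation starts at least one level below the tablet MTD or MAD, so Level 4 suspension is reached only after a higher tablet level or by escalating up to it. The documents do not show that this chart, or Level -1, was ever used. This stands too, and it limits the practical effect.

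The deviation at the two weights is no more than the chart accepts elsewhere. Section 3.3.1.1 treats more than 10% as the point at which tablet dosing "could potentially cause excessive variation in cumulative administered dose per kilogram", but that remark concerns tablets in patients under 20 kg and is not a tolerance for the suspension. It serves only as a sense of scale.

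Finally, the summary of changes reports earlier typographical corrections in Appendix 10. Those concerned the Dose Level 3 and Dose Level -1 suspension charts and leave these errors in place.

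None of this disputes that the heading is wrong or that the two weights lack a single dose.

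**Conclusion.** The concern holds. The Level -1 tablet sub-heading is one third too high (4.2 for 3.15 mg/kg/week), with the title and all rows correct. Two of 370 row-to-row joins are faulty, both in the Level 4 suspension chart: 51.5 kg has no dose and 53.2 kg has two. The consequence is small. Either neighbouring suspension dose is within 2% of target, the two differ by 0.5 mL (2.4 mg/day), and no analysis, DLT count or MTD rule changes. It should still be corrected, because these are binding paediatric dosing instructions that sites may not override with their own arithmetic.

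This rests on two assumptions: that weights are recorded to 0.1 kg, as the bands imply, and that the band limits were read correctly from the PDF. The second is worth a glance at the source page, since the band finding turns on single digits. The heading finding does not depend on that table, because the title and 19 rows independently confirm 3.15.

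**What to change.** In Appendix 10:

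- Dose Level -1 tablets: change the sub-heading to 3.15 mg/kg/week; leave the title and rows unchanged.
- Dose Level 4 suspension: change the 14.5 mL band to 51.5–53.2 kg and the 15 mL band to 53.3–55.0 kg.

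A related slip can be closed at the same time. In the Dose Level 2 tablet chart the last band ends at 126.7 kg and the closing line refers patients above 126.8 kg to the Medical Monitor, so 126.8 kg itself has no instruction. The closing line should start above 126.7 kg. It is a closing line and not a row-to-row join, so it is outside the count of 370.

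The cost is administrative: one heading figure and two band limits, plus the optional closing line, with no change to design, sample size or analysis. The last amendment already made corrections of this kind to the same appendix.
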